## ***RATIONALE FOR THE STUDY***

Robotic therapy is a well-established approach for upper limb rehabilitation in neurological and neurodegenerative populations, allowing clinician teams to increase the intensity and standardization of therapy. A key strength of robotic therapy is the possibility to personalize treatment in real-time based on a patient's performance, offering therapy that tailors the levels of difficulties, intensity, required movements, assistance levels, and workspace according to the patient's progress. This feature not only enhances motor recovery but also improves engagement and motivation, promoting neuroplasticity—a critical factor in the long-term recovery of neurological functions. In a Cochrane Review on cognitive rehabilitation for attention deficits, the authors highlight that improving attention, also in the short term, is very important during motor and functional rehabilitation programs because high attention may enable people to engage better with the exercises proposed with a high ability to cope with proposed tasks. Given the inter-relationship between cognitive and motor functions, improvements in motor skills may not always lead to functional gains in activities of daily living without addressing cognitive impairments. For instance, deficits in attention and executive functioning can hinder a patient's ability to perform daily tasks despite motor recovery. This highlights the necessity for a more integrated approach to rehabilitation that concurrently addresses both motor and cognitive domains. In the last years, robotics rehabilitation, has included exercises stimulating cognitive functions, which can be proposed and performed during motor exercises. Several studies confirmed the high prevalence of cognitive impairment in neurological and neurodegenerative disorders underlining its significant influence on motor learning strategies, functional recovery, and quality of life. Nevertheless, usually, the aim of the robotic treatment is the

improvement in motor performance and activities of daily living, while the cognitive deficits are often ignored or treated separately from motor impairment. A cognitive treatment is crucial for the subjects in which cognitive and motor impairments are often present at the same time, such as neurological patients. Many studies have found that improvements in upper limb motor function do not always lead to progress in activities of daily living, such as dressing or eating. This may be because cognitive impairments, which often accompany motor issues, are not sufficiently addressed. Few studies explored the cognitive effects of a robotic rehabilitation program, and they did not use tools to investigate specific cognitive functions. After upper limb robotic treatment, all the explored cognitive domains significantly improved, such as attention and processing speed, visuospatial abilities, visual memory, executive functions, and memory. The implementation of cognitive tasks within robotic therapy, such as dual-task or feedback mechanisms, has the potential to stimulate cognitive processes directly linked to everyday functioning, including memory, visuospatial abilities, and problem-solving. This can promote neuroplasticity by simultaneously engaging multiple brain networks, thereby promoting broader neurological recovery. Moreover, robotic devices ensure consistent and reproducible therapy. Intensive and repetitive rehabilitation training are essential for regaining motor functions, which can be challenging to achieve with traditional therapy. An adaptive robotic training offers unique advantages for neurological and neurodegenerative patients, as well as the capacity to adjust task difficulty in real-time to ensure the patient remains cognitively engaged. This continuous engagement is essential to improve neuroplasticity mechanisms that support both motor and cognitive recovery. Robotic therapy is not only as effective but potentially more beneficial in specific cases due to its precision and customization. Several studies, including systematic reviews, have shown that robot training not only improves activities of daily living but also enhances muscle strength and function in the affected arm^15. Two recent large-scale studies further support this, demonstrating that robotic therapy is at least as effective as conventional therapy in improving motor outcomes. The most recent meta-analysis suggests that robotics can improve upper limb motor function and muscle strength, and, when compared to a similar amount of conventional therapy, no significant differences in terms of motor recovery are detected. In fact, some research suggests that robotic-

assisted rehabilitation might provide an edge due to its precision and ability to customize the difficulty of each task, offering a personalized and engaging approach. The limited focus on cognitive rehabilitation in existing studies may contribute to better outcomes, as well as patients with concurrent cognitive deficits may not fully benefit from motor rehabilitation alone. A systematic review revealed that only 15% of stroke rehabilitation trials included patients with cognitive impairments, underscoring a significant research gap that needs to be addressed to improve the inclusivity and efficacy of robotic interventions. The efficacy of robotics in recovering cognitive deficits was few explored. To date, the implementation of new graphical interfaces and more ecological scenarios, as well as more cognitively demanding tasks, can allow an active physical and cognitive engagement of patients during robotic therapy, due to a variety of solutions with different levels of technology, assistance, and complexity of exercises. This can be promoted through adaptive assistance, cognitive challenge, visual and auditory feedback to enhance patient's engagement facilitating neuronal reorganization in the motor cortex.

The present study aims to assess the effectiveness of upper limb rehabilitation using robotics and virtual reality, comparing it to conventional therapy. The objective is to demonstrate that this innovative approach leads to more significant improvements in both motor and cognitive outcomes. Both the experimental and control groups will follow a rehabilitation program that involves not only the upper limb but also other body regions. The comparison between the two groups will be based on the analysis of cognitive and motor outcomes achieved in relation to upper limb rehabilitation. Therefore, we hypothesize that a robotic treatment, based on the execution of selected exercises, based on concurrent motor/cognitive tasks can improve cognitive deficits beyond motor function in patients with neurological and neurodegenerative disorder. The current study evaluates the cognitive effects of upper limb robotic rehabilitation training in neurological and neurodegenerative conditions.

## **OBJECTIVES OF THE STUDY**

Assess the efficacy of sensor-based robotic rehabilitation training on cognitive functioning in patients with neurological and neurodegenerative disorders versus conventional therapies.

### **Primary Objectives:**

- Evaluate the effect of robotic rehabilitation on specific cognitive domains (e.g. attention, memory, executive functions, visual-spatial perception) in patients with neurological and neurodegenerative disorders.

### **Criteria for the primary outcome:**

- Parkinson's Disease: The ACE-R (Addenbrooke's Cognitive Examination-Revised) will be used to measure improvement, where significant progress in at least 2 subscales will indicate effective cognitive rehabilitation.
- Multiple sclerosis: The Rao's Brief Repeatable Battery will assess cognitive function, with improvement in at least 2 subscales indicating significant recovery.
- Stroke: The Repeatable Battery for the Assessment of Neuropsychological Status (RBANS) will be used, with a significant cognitive improvement marked by an increase of 10 points.

### **Secondary Objectives:**

- Analyze the correlation between specific cognitive deficits and motor recovery in patients undergoing robotic rehabilitation training
- Investigate the role of motor rehabilitation integrated with cognitive tasks in improving cognitive and motor functions.
- Analyse the impact of robotic rehabilitation on mood and psychological well-being.
- Compare the effectiveness of robotic rehabilitation training among different subgroups of neurological patients (Stroke- Multiple sclerosis- Parkinson's disease).

- Explore the influence of individual patient characteristics (age, severity of cognitive impairment, disease stage) on cognitive rehabilitation outcomes.

## STUDY DESIGN

This study is designed as a randomized controlled trial with parallel groups aimed at evaluating the effectiveness of upper limb rehabilitation using robotics and virtual reality in comparison to conventional therapy. The primary objective is to demonstrate that this innovative approach leads to more significant improvements in both motor and cognitive outcomes.

Both the experimental and control groups will follow a structured rehabilitation program that involves not only the upper limb but also other body regions, ensuring a comprehensive approach to functional recovery. The experimental group will undergo robotic and virtual reality-based training, while the control group will receive conventional therapy. The comparison between the two groups will be based on the analysis of cognitive and motor outcomes related to upper limb rehabilitation, allowing for an in-depth assessment of the potential advantages offered by robotic therapy.

## **METHODS AND PROCEDURES OF THE STUDY**

The current study will follow the following timeline:

*T0. Baseline:* Initially, patients will be recruited and randomly assigned to one of two groups using block randomization. This method divides participants into small blocks and assigns an equal number of patients to each group within each block. For example, in a block of four participants, two will be assigned to group A and two to group B. This process is repeated for each block, ensuring that both groups have a balanced number of participants throughout the study.

SBRR will receive motor and cognitive rehabilitation assisted by robotic and sensor-based devices through Motore, Armeo Senso, Hand Tutor, Armeo Power, Armeo Spring, Pablo, Amadeo, Diego. SCT will receive conventional motor rehabilitation treatment.

Subsequently, patients will undergo a neurological examination, comprehensive neuropsychological assessment, and motor evaluation. These assessments will be conducted in a blinded modality, with evaluators distinct from recruiters and therapists. Importantly, the evaluators will not be aware of the group assignment of the patients.

Following these assessments, both groups will engage in their respective rehabilitation programs. Each session will perform for 60 minutes 2-3 times a week for a total of 25 sessions.

*T1. Post-intervention assessment:* At the end of the rehabilitation program, a comprehensive neuropsychological and motor assessment will be conducted again.

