### **Motor Assessment:**

Each participant will undergo by a motor evaluation before (T0) and immediately after the end of the robotic training (T1). The evaluation will be conducted by physiotherapist. It includes: Fugl-Meyer Assessment – Upper Limb (FMA-UL) comprises of five domains: motor functioning (in the upper and lower extremities), sensory functioning, balance, joint range of motion and joint pain. It includes items assessing movement, coordination, and reflex action of the shoulder, elbow, forearm, wrist, hand; Motricity Index (MI) for the upper limb assess upper extremity function and functional mobility; Disability of the Arm, Shoulder and Hand (DASH) assesses musculoskeletal disorders of the shoulder, hand and arm; Nine Hole Peg Test (9HPT) and Box and Block Test (BBT) measure unilateral gross manual dexterity; Test del monofilamento di Semmes Wilson assesses whether alterations in skin sensitivity are present.

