### **Inclusion criteria**

- Age 18-75 years;
- FMA-UL 0-31: eligible for exoskeletons and robotic devices with high support. (Armeo Power, Amadeo, Motore)
- FMA-UL 32-47: eligible for end-effectors with medium support. (Armeo Spring, Hand Tutor, Diego)
- FMA-UL 48-52: eligible for sensor-based with low support. (Pablo, Diego, Armeo Senso)
- MoCA: ≤20

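### Random allocation is placed before the T0 assessments, so the baseline used in the ANCOVA and the pre-post tests is a post-randomisation, though pre-treatment, measurement

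*Protocol*

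**What the plan says.** Only the protocol is at hand. Its section Methods and Procedures of the Study introduces a sequence: "The current study will follow the following timeline". Under T0 the steps are:

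1. "Initially, patients will be recruited and randomly assigned to one of two groups using block randomization".
2. "Subsequently, patients will undergo a neurological examination, comprehensive neuropsychological assessment, and motor evaluation".
3. "Following these assessments, both groups will engage in their respective rehabilitation programs".

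Between the second and third steps it describes blinding of those who test: "Importantly, the evaluators will not be aware of the group assignment of the patients". It also says that evaluators are separate from recruiters and therapists.

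The Cognitive Assessment and Motor Assessment sections define T0 relative to the training only. Neither relates it to randomisation.

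Statistic Analysis uses T0 in three ways: as the reference for the paired T0-T1 tests within each group, in an unpaired comparison of the groups at T0, and as the cognitive covariate (with age) in the ANCOVA of T1 cognitive scores.

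**The concern.** A baseline measured before allocation is independent of arm by design, and any difference between the arms at that time is chance. A baseline measured after allocation does not have this property automatically. If patients already know whether they will get robotic or conventional therapy, that knowledge could affect effort or mood during the T0 tests.

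The ANCOVA is meant to isolate the effect of the rehabilitation method from baseline differences. If T0 itself depends on arm, adjusting for it moves the estimated group effect instead of cleaning it. The within-group change scores and the improvement criteria for the primary outcome, such as the 10-point RBANS increase in stroke, would start from the same affected value.

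**Working it through.** The protocol gives no figure on this point, so the check is a reading of the sections against each other, plus one formula.

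**Step 1: the order.** The T0 paragraph uses three successive time markers: allocation first, assessments next, treatment last. T0 therefore lies after randomisation and before treatment. The statement that evaluators do not know the assignment fits an assignment that already exists at that time.

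**Step 2: does another section correct the order?** Cognitive Assessment and Motor Assessment say only that T0 precedes the training, which is true under either order. Study Population requires the inclusion criteria to be met before patients are divided into groups. That places eligibility before allocation, but says nothing about the T0 batteries. No section puts T0 before randomisation.

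**Step 3: by which routes could T0 depend on arm?**

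| Route | What the protocol says | Status |
|---|---|---|
| Effect of treatment | Treatment follows the T0 assessments | Excluded |
| Evaluator expectation | Evaluators blinded and separate from recruiters and therapists | Reduced |
| Patient's knowledge of the arm | No statement on when patients learn their group | Open |

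**Step 4: what the open route would do.** Suppose that knowing the arm shifts mean T0 in one arm by δ, and T1 is unaffected. The ANCOVA group effect is

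(difference in mean T1) − *b* × (difference in mean T0) − (age term),

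where *b* is the within-group slope of T1 on T0. A constant shift within one arm leaves *b* and the age term unchanged, so:

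- the ANCOVA group effect moves by −*b*δ;
- the mean T0-T1 change in that arm moves by −δ.

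The protocol gives neither *b* nor δ. If δ = 0, both movements are zero. A numerical bias could be obtained only by assuming both inputs, and none is offered.

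**Step 5: effect on sample size.** None. The planned numbers do not depend on the order of T0 and allocation.

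**The case against.** The strongest defence is that the route is narrow. T0 precedes treatment. Evaluators are blinded. The primary instruments (ACE-R, Rao's battery, RBANS) are neuropsychological tests given by a neuropsychologist and not self-report questionnaires. No interval between allocation and T0 is stated. The information sheet mentioned under Informed Consent is not shown and may say when patients learn their group. The wording may also be loose, with baseline first in practice. All of this stands, and it is why the point is minor. It does not remove the point, because the written order leaves the patient's knowledge of the arm uncontrolled at T0.

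A reader might infer two stronger points, which the protocol does not support.

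- *Patients lost between allocation and T0 damage the analysis.* One might count the margin between the 52 needed and the 63 planned per group (63 − 52 = 11, if the garbled sample-size sentence means 63 per group) as at risk. But treatment starts only after T0, so a patient lost before T0 would normally have no T1 either. A pre-allocation baseline would not return that patient to the paired test or to a complete-case ANCOVA. The margin is the general dropout allowance and is not specific to this issue.
- *The FMA-UL timing is contradictory*, because it belongs to the T0 motor evaluation and is also an inclusion criterion ("FMA-UL 0-31: eligible for exoskeletons and robotic devices with high support"). Study Population already puts eligibility before grouping, and using one instrument at screening and again at T0 is consistent with that. MoCA is an inclusion criterion that appears in none of the T0 batteries, so some eligibility testing outside them is already implied. Whether the screening FMA-UL is reused as the T0 value is an unspecified detail, not an error.

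**Conclusion.** The point holds as a minor one. As written, the T0 cognitive scores used as ANCOVA covariate and pre-post reference are measured after randomisation and before treatment, and nothing shown guarantees that they are independent of arm. The size and direction of any bias are unknown and may be zero.

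The conclusion rests on two assumptions: that the T0 paragraph means the order it states, and that no document outside the protocol keeps patients unaware of their group until T0 is done. If either fails, only a clarification of wording remains. A reader should not conclude that the trial's baseline is biased or that ineligible patients would be randomised. The protocol shows neither.

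**What to change.** Reword the T0 paragraph of Methods and Procedures of the Study to fix this order:

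*Eligibility is confirmed. All T0 neurological, neuropsychological and motor assessments are then completed. Only after that is the patient randomised and told the allocation. Treatment starts thereafter.*

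If the order cannot change, add:

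*Patients will not be told their group until all T0 assessments are complete.*

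Either version stops the patient's knowledge of the arm from affecting T0. Neither addresses expectation effects at T1. While editing, the sponsor could note whether the screening FMA-UL also serves as the T0 value.

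**Cost.** Reordering means T0 testing of some patients who withdraw before randomisation, and possibly some rescheduling of the T0 battery. The fallback needs staff to withhold the allocation until T0 is done, with no change to visits or tests. Sample size, analyses and treatment are unaffected.

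### Allocation is drawn before the T0 assessments, and the block scheme seeks only overall balance, so balance within stroke, MS and Parkinson's disease is not guaranteed

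*Protocol*

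**What the plan says.** **Order.** In the Methods and Procedures section, under T0, "patients will be recruited and randomly assigned to one of two groups using block randomization". The next step reads: "Subsequently, patients will undergo a neurological examination, comprehensive neuropsychological assessment, and motor evaluation".

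**Blocks.** The scheme "assigns an equal number of patients to each group within each block". Four is the only size mentioned, and only as an illustration: "in a block of four participants, two will be assigned to group A and two to group B". The stated aim is "ensuring that both groups have a balanced number of participants throughout the study". Neither stratification by disease nor concealment of the list is described.

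**Masking.** Assessments are blinded, "with evaluators distinct from recruiters and therapists". Nothing is said about when patients or therapists learn the arm.

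**Where the diseases come in.** The primary outcome criteria use a different instrument for each disease: ACE-R for Parkinson's disease, Rao's battery for MS and RBANS for stroke. A secondary objective compares the three diseases. The between-group ANCOVA (Statistic Analysis) adjusts for the T0 cognitive score and age, not for diagnosis.

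**Entry.** FMA-UL bands are inclusion criteria, and FMA-UL is also part of the T0 motor assessment. The exclusion criteria (severe cognitive, behavioural and sensory disorders) have no definitions. The Study Population section, however, has subjects meet all inclusion criteria before they are divided into groups.

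**The concern.** Two separate matters are at stake.

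1. **Baseline measured after allocation.** Robotic and conventional therapy cannot be hidden from those who give or receive them. If the arm is known when T0 is recorded, effort on cognitive tests, attendance at the baseline visit or willingness to stay can differ by arm. The T0 scores are then no longer a pre-randomisation covariate, and adjusting for them can carry the difference into the estimated effect. Discretion in applying undefined exclusions makes a clean order of steps more important.

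2. **Balance where the comparison is made.** Because the instruments differ, the cognitive comparison is in effect made within each disease. Blocks that balance only the overall arm sizes leave the split within each disease to chance, and a pooled model without diagnosis does not correct for an uneven mix.

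**Working it through.** **Inputs.** From the protocol: d = 0.4, two-sided alpha 0.05, power 0.80, 52 per group, 20% dropout, and an adjusted figure printed as 63 per 3 per group. Assumed: three diseases of equal size, random order of arrival, blocks of four.

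**The plan's own figure.** A paired t-test at d = 0.4 has power 0.7999 with 51 patients and 0.808 with 52, so 52 reproduces. 52 × 1.2 = 62.4, rounded up to 63 (dividing by 0.8 would give 65). The printed 63 per 3 can mean 63 per group (N = 126, 42 per disease) or 63 per disease per group (N = 63 × 3 × 2 = 378, 126 per disease). Both are carried below. The protocol gives no figure for balance within disease or for predictability.

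**T0 after allocation.** Let δ be the shift in mean T0 score between arms caused by knowing the arm, and β the ANCOVA slope on T0. If T1 is unaffected:
- the ANCOVA estimate moves by −βδ;
- a comparison of change from T0, such as the 10-point RBANS criterion, moves by −δ;
- a plain T1 comparison does not move.

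The protocol gives no basis for δ, so no size can be stated.

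**Balance within a disease, one list for all.** With n of N patients in a disease, the number in one arm has approximate variance n × ¼ × (N − n)/(N − 1). The arm difference has twice that SD, and its mean absolute value is about 0.80 × SD.
- N = 126: variance 42 × 0.25 × 84/125 = 7.06; SD of the difference 2 × 2.66 = 5.3; mean about 4.2.
- N = 378: variance 126 × 0.25 × 252/377 = 21.1; SD of the difference 2 × 4.59 = 9.2; mean about 7.3.

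Simulation of 4,000 trials per setting agrees:

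| | N = 126 | N = 378 |
|---|---|---|
| Mean arm difference within a disease | 4.2 | 7.4 |
| 95th percentile | 10 of 42 | 18 of 126 |
| Any disease off by 20% or more of its patients | 20.6% | 1.6% |
| Largest difference, blocks of four split by disease | 2 | 2 |

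At 42 per disease, a difference of 10 (26:16) is the first even number above 20% of 42 = 8.4, so 20.6% is also the chance that at least one disease is off by 10 or more. For a given disease that chance is 8.6%.

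**Cost in power.** Two-sample t-test within a disease, d = 0.4, noncentrality d/√(1/n₁ + 1/n₂):
- 21:21 gives 0.4/√0.0952 = 1.30, power 0.244; 26:16 gives 0.4/√0.1010 = 1.26, power 0.233.
- 63:63 gives power 0.606; 72:54 gives 0.597.

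The loss is about 0.01 in each case.

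**Predictability, if blocks were fixed at four and allocations tracked.** There are six equally likely orders. The fourth allocation is always certain, and the third is certain in two orders of six: (1 + 1/3)/4 = 33.3%. Best guesses are right with probability 1/2, 2/3, 2/3 and 1 at the four positions: 2.833/4 = 70.8%, against 50% by chance. For blocks of six the rate is 68.3%. Mixing sizes 4 and 6 equally often gives (4 × 0.708 + 6 × 0.683)/10 = 69.3%; simulation gave 69.2%.

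**The case against.** Three stronger readings are tempting, and the protocol does not support them.

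- **That recruiters can foresee allocations.** Four is introduced as an example, with generic group labels. The 33% and 71% figures need a fixed block of four and recruiters who see every past allocation, and the 33% also needs the size to be known. None of this is stated. Leaving the true size out of a protocol is good practice, and concealment details may sit in a document not shown. Drawing the allocation before T0 does not make it more foreseeable either.
- **That patients can be admitted or rejected once the arm is known.** The Study Population section puts fulfilment of the inclusion criteria before division into groups. MoCA is in none of the T0 batteries, so it appears to be a screening measure. Only FMA-UL is both an entry criterion and a T0 measure, and the T0 evaluators do not know the group.
- **That the disease-level comparisons are biased or badly weakened.** Chance imbalance in numbers does not bias a comparison within a disease, and the power loss is about 0.01. The protocol is silent on stratification, which is weaker than declaring an unstratified list. If the target is 378, marked imbalance is rare.

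All three replies stand. They do not remove the stated order of allocation and T0, the stated aim of overall balance only, or the absence of diagnosis from the ANCOVA. Evaluator blinding protects scoring; it does not protect the patient's effort, attendance or retention.

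**Conclusion.** The point holds in a limited form. As written, T0 follows allocation, so the baseline covariates are not protected from knowledge of the arm. This assumes that patients or therapists learn the arm before T0 is complete, which the protocol neither states nor excludes, and the size of any effect cannot be computed. The block scheme as described does not guarantee balance within disease. Under equal disease sizes and blocks of four, the mean arm difference is about 4 of 42 patients, with a 21% chance that some disease is off by 10 or more if N = 126. The chance that any disease is off by 20% or more of its patients is about 2% if N = 378. This is a matter of precision and tidy design, not of bias within a disease; it matters more for a pooled model that omits diagnosis. If 63 per disease per group is the target, a single list cannot ensure it. Predictability is a conditional risk (at most 33% certain and 71% guessed under a fixed, tracked block of four), not a demonstrated fault.

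**What to change.** 1. Reorder the T0 step: record eligibility, including FMA-UL and the exclusions, and complete all T0 assessments before the allocation is drawn.
2. Use a separate permuted-block list for stroke, MS and Parkinson's disease.
3. Include diagnosis as a factor in any pooled ANCOVA.
4. State that the list is concealed from recruiters, for example by central release one patient at a time, with block sizes undisclosed. Varying the size is not enough alone, since it lowers correct guessing only from about 71% to about 69%, and splitting the list by disease does not lower it.

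**Cost.** A new computer-generated list and a reordered step at T0; no extra patients. Overall balance is slightly looser: with blocks of four the arms can differ by up to 2 per list, so by up to 3 × 2 = 6 over three lists, against 2 with one list.
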